### **11.3 Statistical criteria of termination of trial**

There are no plans for early termination of the trial.

### **11.4 Planned Analyses**

#### **11.4.1 Datasets to be analysed, analysis populations**

Primary analysis of the primary outcome will be based on the intention-to-treat (ITT). The ITT population will include all participants with associated primary outcome data, excluding only subjects who were deemed ineligible following the screening visit, those who withdrew from the trial and were unwilling for their previously collected data to be utilised or those who failed to provide baseline.

#### **11.4.2 Primary Analysis**

The study will assess the performance of the IP in comparison to the SP using a preference questionnaire. After wearing the devices for at least 10 +/- 7 days and using them in daily life and various music situations, the subjects will be asked to complete a preference questionnaire and choose between the two music programs (SP and IP).

The preference score is rated on a 5-points Likert scale: SP much better, SP better, no difference, IP better, IP much better. The score distribution is described by the minimum, median, and maximum values and tested with a Wilcoxon signed-rank test with the assumption that ordinal scores from a Likert scale reflect the within subject difference. The null hypothesis is that there is no difference between the tested protocols and the alternative hypothesis is that there is a preference for a protocol. A two-sided test will be made as the IP has not been tested before.

Certainty and motivation of preference will be summarized and described separately. The results of this test will be used to answer the 1st and 2nd research questions.

#### **11.4.3 Secondary Analyses**

The secondary objective is to assess the perception of music with the IP in comparison to the SP using the adaptive music perception (AMP) test (Kirchberger & Russo, 2015). The AMP provides a means to

evaluate perception of details in music with various subscales, e.g. pitch, duration, loudness. The hypothesis is that the performance of the IP should not be inferior to that of the SP. Baseline scores for the AMP test are measured unaided and aided with the general listening program, i.e. not specific for music.

The AMP test is based on an adaptive procedure that provides the threshold reflecting the amount (time, loudness, pitch...) that each participant can detect above chance. The thresholds are measured on ratio scales: duration in milliseconds, pitch in hertz, loudness in decibels. Kirchberger & Russo (2015) indicate that the thresholds might be influenced by different covariates, like degree of hearing loss or music experience, and by the type of signal processing. Measured thresholds will therefore be modelled by a linear mixed-effect regression with backwards selection based on the variation inflation factor (VIF). This gives a complex picture for the coefficient interpretation as there are 4 test conditions: unaided, aided general program, aided SP, and aided IP. Planned contrasts will be considered:

1. Unaided vs Aided
2. General vs Music-specific programs
3. IP vs SP

The 3rd research question will be answered with a paired t-test on each subscale comparing threshold from the IP to the thresholds from the SP.

Additionally, a music perception questionnaire based on Rutledge (2009) will evaluate the perception of music in various environments with each listening program. Overall hearing aid benefit will be measured with a general product questionnaire

The results from the music questionnaire are scores from a visual analogue scale. The distribution of the scores will be visualized with boxplots for each listening program (General, IP, or SP program) and focus (own musical instrument vs other musical instruments). The effect of listening programs and focus will be evaluated with mixed effect regression model taking into account the hearing loss degree, own instrument category (string, woodwind, or brass), and music experience as fixed effects. Planned contrasts will be considered:

1. General vs Music-specific programs
2. IP vs SP

Results from the second contrast will be used to answer the 3rd research question.

#### **11.4.4 Interim analyses**

There are no plans for an interim analysis.

#### **11.4.5 Safety analysis**

The questionnaires used for the secondary outcome will also contain questions to measure the safety of the devices. These questions will specifically address unexpected noise or behaviour from the devices. Unexpected behaviour includes unprovoked feedback or whistling, distorted sounds or artefacts, spontaneous muting or the shutting off of the device, and any unexplained warning signals, beeps, or loud sounds.

The adverse event risks of taking part in the study have been assessed to be low. Numbers of adverse events and serious adverse events will be cross-tabulated for the IMD and categorised by severity. No formal statistical analysis will be conducted, but AEs and SAEs will be closely monitored throughout the process.

#### **11.4.6 Deviation(s) from the original statistical plan**

Due to the home-based nature of the trial, it is possible that there will be a few deviations from the study protocol, e.g. not wearing hearing aid, manipulation issues, misplacement, etc.

As well as non-compliance with the protocol, there could be other protocol deviations, for example if follow-up assessments take place outside the pre-specified  $\pm 10$  days window. The numbers and proportions of participants with protocol deviations will be summarised with details of type of deviation provided. No formal statistical testing will be undertaken.

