## 6. STUDY DESIGN

This is a controlled, single blinded, comparative clinical evaluation conducted monocentric at the premises of Bernafon AG in Bern, Switzerland.

The exploratory study is based on a population of 18-20 hearing impaired people that have a hearing loss appropriate for the IMD.

As the comparator, the subjects will be fit with an SP in the same hearing aid as the IP. Additionally, a control situation will be the P1 or general program that is intended for all daily listening situations excluding music giving the subjects 3 programs within the IMD.

There is no placebo or device that does not provide amplification. The study consists of two field and three lab tests. A randomized and single-blinded, single-arm design will be used for the field tests. The lab test order will be randomized and single-blinded.

The study will consist of hearing-impaired subjects with hearing loss ranging from mild to profound and appropriate for testing of the IMD. The lab testing (AMP) will be single blinded and randomised and performed in a simulated environment. The blinding and randomization refer to the position that the SP and IP have within the programming. When multiple programs are fitted to the hearing aid the subject switches programs with a button that scrolls through the programs. The subjects will not know if the SP or the IP are in second or third position during both the field and the lab testing.

The subjects are expected to participate for approximately 1 month. The testing will include a combination of a field and lab tests. There are three lab tests during which the participants will not spend more than 2 hours in the clinic (including breaks). The field test periods will not last more than 10 +/- 7 days.

The sequence for the testing will begin with the screening appointment in which participants are invited to the clinic to determine if they are candidates for the trial. The entire test procedure will be

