## **8. STUDY INTERVENTION**

### **8.1 Identity of Investigational Products (medical device)**

The treatment will be approximately 20 days of use with the devices. For the first field test of 10 +/- 7 days they will use the devices to become accustomed to the amplification. For the second field test lasting 10 +/- 7 days they will use the devices with an additional two programs (IP and SP) to try when listening to music.

There will be three lab tests (one at each appointment) during which the participants will use the IMD, for up to 2 hours during testing in the clinic.

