#### **9.3.2 Fitting/Second visit**

Fitting Visit, Day 10 +/- 7: Otoscopy is performed, and the subjects return the completed questionnaires. The IMDs are fitted with IP and SP as specified by the randomization carried out at the first visit. The IP is optimized and fine-tuned based on comments that the subject makes about the sound while they play their instrument in the clinic. The SP is programmed without any adjustment based on the default music program offered in the software. They are instructed to switch between programs two and three when playing and listening to music for the next 10 +/- 7 days. They perform the lab test with the AMP in one condition: aided with P2. The subjects are given the music perception questionnaires and instructed to complete them at home a day before their next appointment. One questionnaire pertains to P2 and the other to P3. Any AEs are reported in the CRF. They are scheduled for the third visit.

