#### **9.3.3 Lab/Third visit**

Final Visit, Day 20 +/- 7: Otoscopy is performed. The subjects return the completed product questionnaires. They perform the lab test with the AMP in one condition: aided with P3. They complete a preference questionnaire during the appointment. They are notified that the trial has ended and those that normally wear hearing aids can return to using their own devices. They will return the IMD to the clinic. Any AEs are reported in the CRF. Those that are on the Bernafon subject list and normally wear devices fitted by the Bernafon clinic are reminded to return to the clinic for normal maintenance of their hearing aids. Anyone that would like to join the Bernafon clinic are also welcome to do so.

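### The ±10-day window in Protocol 11.4.6 matches no visit window in the plan, and the visit windows do not secure the stated length of the second field period

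*Protocol*

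**What the plan says.** **Deviation window.** Protocol 11.4.6 lists home-use problems and non-compliance as deviations. It then adds, as an example, the case "if follow-up assessments take place outside the pre-specified" window of ±10 days. Numbers, proportions and types of deviation will be summarised, without formal testing.

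**Visit windows.** Protocol 9.3.2 sets "Fitting Visit, Day 10 +/- 7" and 9.3.3 sets "Final Visit, Day 20 +/- 7". The Study Schedule and the table in 9.1 give the same figures, with screening as day 0.

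**Field-period length.** Protocol 8.1 and 8.2.1 give each field period as 10 ± 7 days. In 9.3.2 the second one starts at visit 2, when the optimized (IP) and standard (SP) music programs are fitted.

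**Ceiling or floor.** Protocol section 6 says "The field test periods will not last more than 10 +/- 7 days". Protocol 11.4.2 describes the preference as given "After wearing the devices for at least 10 +/- 7 days and using them in daily life and various music situations". Protocol 4.2 and SAP 6.1.1 carry the same minimum wording.

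**Use of the interval.** The preference questionnaire, which is the primary outcome, is completed at visit 3 after both programs have been used in the second field test (Protocol 9.2.1, 9.3.3).

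**The concern.** A window described as already specified should be found elsewhere in the plan, and this one is not. Anyone compiling the deviation table from 11.4.6 would use a wider tolerance than the schedule allows, and two people working from different sections would classify the same dates differently.

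The second issue is exposure. The time between visits 2 and 3 is the participant's only field experience of IP and SP before choosing between them. If the visit windows do not control that interval, and the text calls it both a maximum and a minimum, a reader of the report cannot tell what experience a stated preference rests on. With 18–20 participants, one person is 5% to 5.6% of the primary data (1/20 to 1/18).

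**Working it through.** **Inputs**
- Visit 2: day 10 ± 7, so days 3–17 (Protocol Study Schedule, 9.1, 9.3.2).
- Visit 3: day 20 ± 7, so days 13–27 (Protocol Study Schedule, 9.1, 9.3.3).
- Each field period: 10 ± 7, so 3–17 days (Protocol 8.1, 8.2.1).
- Deviation example: ±10 days (Protocol 11.4.6).

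**Step 1: can ±10 be reproduced?** The visit windows give ±7 and the field-period tolerance gives ±7. Two field periods in sequence give (10 + 10) ± (7 + 7) = 20 ± 14. None of these is ±10.

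**Step 2: what ±10 would miss.** I assume that ±10 applies around the nominal days.
- Visit 2: 10 ± 10 = days 0–20, against days 3–17. Days 0–2 and 18–20 are off schedule but inside ±10. Day 0 is the screening day itself, so that value is a formal limit only.
- Visit 3: 20 ± 10 = days 10–30, against days 13–27. Days 10–12 and 28–30 are off schedule but inside ±10.

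**Step 3: the second field period implied by the visit windows.** Write visit 2 = 10 + a and visit 3 = 20 + b, with a and b whole numbers from −7 to 7. Then

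gap = 10 + (b − a).

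There are 15 × 15 = 225 pairs, and 15 − |d| of them have b − a = d.

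| Gap (days) | d = b − a | Pairs |
|---|---|---|
| below 0 (visit 3 before visit 2, impossible) | −14 to −11 | 1 + 2 + 3 + 4 = 10 |
| 0 to 2 | −10 to −8 | 5 + 6 + 7 = 18 |
| 3 to 17 | −7 to 7 | 169 |
| above 17 | 8 to 14 | 7 + 6 + 5 + 4 + 3 + 2 + 1 = 28 |

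Feasible pairs: 225 − 10 = 215. Of these, 18 (18/215 = 8.4%) fall short of 3 days, 5 of them at zero, and 28 (28/215 = 13.0%) exceed 17 days. The longest gap is 27 − 3 = 24 days. As a concrete case, visit 2 on day 17 and visit 3 on day 18 are both inside their windows, with a gap of 18 − 17 = 1 day.

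**Step 4: the reverse direction.** Two field periods of 3–17 days put visit 3 between 3 + 3 = day 6 and 17 + 17 = day 34, against a window of days 13–27. Of the 225 combinations, 28 are too early and 28 too late for the visit 3 window.

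**Step 5: ceiling against floor.** Section 6 makes 10 ± 7 an upper limit; 4.2, 11.4.2 and SAP 6.1.1 make it a lower limit. Read literally, a range cannot serve as both, and a minimum stated as a range does not say which end binds.

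**The case against.** The strongest reply is that little turns on this.

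- The window in 11.4.6 is introduced as an example, and general non-compliance is listed beside it. It is not an exclusive rule. This stands, although the example still relies on a figure found nowhere else.
- The visit windows and the field-period length can be met together: 169 pairs satisfy both. They are not incompatible. This stands too. The defect is that meeting the first does not secure the second, and no section says which governs.
- A reader might infer that a participant with no usable second field period counts as fully on protocol. The documents do not support that. A gap of 0–2 days satisfies the visit windows and the 11.4.6 timing example, but it breaches the field-period length in 8.1, 8.2.1 and 9.3.2.
- Data logging (Protocol 8.2.1, 8.4) records hours in each program, so low use would be noted. This is a real safeguard, but it has no threshold and no stated consequence for the analysis.
- The minimum wording has a natural reading of 3 days. That is plausible, but the text does not say so, and section 6 uses the same interval as a maximum.
- The pair counts are not forecasts. Nothing suggests that visits will fall at opposite edges of their windows.

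**Conclusion.** The point holds as an inconsistency in a reporting rule and an unreconciled exposure interval for the primary outcome. The ±10 figure has no source in the plan and would leave up to three days at each edge of each visit window uncounted by the timing example. The visit windows permit second field periods from 0 to 24 days, against a stated 3 to 17.

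This rests on whole-day counting, on visit 3 not preceding visit 2, and on ±10 being centred on days 10 and 20. The shares of 8.4% and 13.0% describe permitted date pairs and should not be read as expected proportions of participants.

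A reader might also infer that the primary result is at risk. It is not, on this ground: the ITT set (Protocol 11.4.1, SAP 4.2) has no timing or exposure criterion, so the window removes nobody, and the Wilcoxon test is unaffected. What is affected is the accuracy of the deviation table and how far a stated preference can be interpreted as following a known period of use. SAP section 5 also names a per-protocol population without a timing definition, so it does not settle the matter.

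**What to change.** Reconcile the Study Schedule, Protocol 4.2, 6, 8.1, 8.2.1, 9.1, 9.3.2, 9.3.3, 11.4.2 and 11.4.6, and SAP 6.1.1, so that visit windows, field-period length and deviation window agree. The figures are for the sponsor to choose. Specifically:

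1. Have 11.4.6 cite the same window as the schedule.
2. Have 11.4.6 also count as a deviation any visit 2-to-3 interval outside the stated field-period length.
3. Remove the conflict between the maximum wording in section 6 and the minimum wording in 4.2, 11.4.2 and SAP 6.1.1.

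If the field-period figure changes, the synopsis must follow. The cost is wording in the protocol and SAP. No visits, participants or assessments are added, and visit dates are already source-verified for all participants (Protocol 12.3), so the interval can be computed from existing data.

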#### **11.5 Handling of missing data and drop-outs**

Unless specified otherwise in each objective, no statistical techniques will be used to impute missing data. If a subject's data are missing for any reason, that subject will not be included in that portion of the analysis. The number of subjects included in each analysis will be reported so that the potential impact of missing data can be assessed.

## 12. QUALITY ASSURANCE AND CONTROL

The Sponsor is responsible for implementing and maintaining quality assurance and quality control systems with written SOPs and Working Instructions. The PI is responsible for proper training of all involved study personnel.

### 12.1 Data handling and record keeping / archiving

Data will be archived with an electronic data management system. The subjects will be given numbers to maintain anonymity. There are also hard copies of subjects' charts that are kept in a locked file cabinet inside of the clinic room. Only the PI, statistician, Monitor, and Auditor will have access to the information. The information will always be archived under the identification number with a key to the identification codes stored in another location (described in chapter 2.8).

#### 12.1.1 Case Report Forms

Participant identities are coded using a participant identification number.

The PI will enter protocol defined data into a web based Electronic Case Report Forms using an EDC-software that conforms to 21 CFR Part 11 (FDA guidance) requirements. Site staff will be given access to the EDC system after a training. The data are checked automatically for plausibility and discrepancies. The generated appropriate error messages allow the data to be confirmed or corrected before being saved in the database. At the end of the study, the PI must certify that the data entered into the Electronic Case Report Forms are complete and accurate. After database lock, the PI will receive a CD-ROM of the patient data for archiving at the site.

The CRF contains the following information:

Field	Author
Participant identification number	PI
Date of visit	PI
Subject birth year	PI
Date of Informed Consent	PI
Age	PI
Sex	PI
Otoscopy	PI
Standard audiology	PI
Hearing loss classification	PI
Eligibility	PI
Trial information provided	PI
Inclusion / Exclusion Criteria	PI
Ear disease	PI
Hearing loss onset	PI
Musical history	
Real ear measure	PI
Investigational device serial numbers	PI
Randomization Program 2	PI
AMP results	PI

Questionnaires received	PI
IFU received	PI
Questionnaires returned	PI
Randomization assignment	PI
Devices returned	PI
Results from music questionnaire	PI
Results from preference questionnaire	PI
Results from product questionnaire	PI
AEs / SAEs, ADE / SADE	PI
Next appointment	PI
Name, date, signature of PI	PI

### 12.1.2 Specification of source documents

The Principle Investigator will maintain adequate and accurate records to enable the conduction of the study to be fully documented and the study data to be subsequently verified. These documents will be classified into two different categories: PI's file, and subject clinical source documents. There will be a PI file or Investigator Site File (ISF) as well as corresponding subject files with source documents.

The PI's file will contain the CIP/amendments, IB/Instructions for use, CRFs, site standard operation procedures (SOPs) or reference to it, EC and CA approval with correspondence, informed consent, device records, staff curriculum vitae and authorization forms, screening and enrolment logs, site-specific subject identification code logs, and other appropriate documents/ correspondence as required by EN ISO 14155 and local regulations.

Subject clinical source documents include, but are not limited to subject clinic records, investigator's notes, appointment book, hearing test results, questionnaires, consultant letters, visit dates, signed Informed Consent Forms, randomisation numbers, SAEs, AEs, etc.

These two categories of documents must be kept on file by the PI for 10 years. If source documents are not durable as long as needed, they must be preserved as a copy. When source documents are required for the continued care of the subject, appropriate copies should be made for storing outside of the site. The information will always be archived under the identification number with a key to the identification codes stored in another location (described in chapter 2.8).

For each subject enrolled an encoded electronic CRF must be completed and e-signed by the PI. This also applies to those subjects who fail to complete the study. If a subject withdraws from the study, the reason must be noted on the CRF.

Case report forms are to be completed immediately after the visit.

Source data corrections will only be performed by study site staff, authorized by the PI. All forms should be completed using a blue permanent pen and must be legible. Errors should be crossed out but not obliterated, the correction inserted, and the change initialled and dated by the PI, co-PI or other investigator.

The entries will be checked by the Monitor and any errors or inconsistencies will be checked immediately. The Sponsor will collect original completed eCRFs on a USB flash drive at the end of the study. The USB flash drive with the completed and e-signed CRFs will remain on site and archived.

Source data must be available at the site to document the existence of the study participants. Source data must include the original documents relating to the study, as well as the medical treatment and medical history of the participant.

### **12.1.3 Record keeping / archiving**

All study data must be archived for a minimum of 10 years after study termination or premature termination of the clinical trial.

Trial documentation is stored in water- and fire-resistant locked boxes in the basement of the Sponsor's building.

## **12.2 Data management**

A Data Management Plan is created by the Statistician according to the Sponsor's SOP ID103. This plan can be found in the TMF.

### **12.2.1 Data Management System**

The CRFs in this trial are implemented electronically using a dedicated electronic data capturing (EDC) system, called Smart Trial. Smart Trial is designed according to IEC62304 and ISO13485 quality standards. The statistician creates the eCRFs and sets up the system for each trial. He then validates the system and records the validation in a report which is stored in the TMF. The EDC system is activated for the trial only after successfully passing this test procedure.

Data is coded when extracted for the analysis. The code values are found in the Codebook located in the TMF.

All data entered in the eCRFs are stored on a Windows server in a dedicated database located in Denmark.

